Effect Of Probiotic Supplementation on The Immune System in Patients with Ulcerative Colitis in Amman, Jordan

By

[name]

Supervisor

[name] [name]

Co-Supervisor

[name] [name]

Funded by the University of Jordan

22 November 2023

NCT04223479

Statistical Analysis

Statistical analyses were performed using Statistical Package for Social Science (IBM® SPSS® Statistics; Version 21.0, version for Windows, 2019, USA). Mean and standard deviation (SD) were calculated for the continuous variables. Frequencies and percentages were used to describe categorical variables. The frequency of participants in terms of categorical variables was compared using the X² test. To check the normal distribution of continuous variables, the Shapiro-Wilk test was applied. Independent samples T-test was used to detect differences between placebo and probiotics groups in terms of continuous variables. A paired t-test was used to assess withingroup changes in biochemical parameters (IgG, IgM, IgA, IL-1, IL-6, IL10, TNF-α, and CRP) from baseline to the end of the study. A p-value < 0.05 was considered statistically significant. All outcomes were calculated by intention-to-treat (ITT) and perprotocol (PP) analyses. For ITT analysis, all randomized patients who took at least one tablet of study medication were included. For PP analysis all protocol violators (patients' dropout or loss of follow-up) were excluded.

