Probiotics also found to have an effect in inducing, maintaining and increasing the remission period in UC and this effect suggested to be also associated with the immunomodulator role of certain microorganisms (Tamaki *et al.* 2016). For example, *in vitro* studies, *Lactobacillus casei* strain Shirota found to have anti-inflammatory effect by inhibition of IL-6 and interferon c (IFN-c) synthesis in lipopolysaccharide (LPS)-stimulated murine chronic IBD cells (Matsumoto *et al.* 2005), and *Lactobacillus delbrueckii* had anti-inflammatory effect by inhibition of NF- κ B pathway in large intestinal lamina propria mononuclear cells (Santos Rocha *et al.* 2012). *In vivo*, *Lactobacillus delbrueckii* and *Lactobacillus fermentum* supplementation, in UC patients undergoing treatment with sulfasalazine (an anti-inflammatory medicine) showed a reduction in several pro-inflammatory parameters in the colon, such as IL-6 levels, tumor necrosis factor TNF- α and NF- κ B p65 expression, and leukocyte recruitment, in comparison with the placebo and medical treatment groups (Hegazy and El-Bedewy 2010). In another study where *Bifidobacterium breve* was administrated as a part of a symbiotic, the results showed a significant decrease in the inflammatory parameters and improvement in the clinical status evaluated by colonoscopy in patients with mild to moderate UC (Ishikawa *et al.* 2011). Moreover, administration of probiotic product Bifid Triple Viable, that contains *Lactobacillus acidophilus*, *B. bifidum* and *Streptococcus*, for 2 months, lead to reduce the expression of IL-1b and increased the expression of IL-10 and immunoglobulin A (IgA) in the colon of UC patients (Li *et al.* 2012).

Materials and Methods:

Study Design

An interventional double-blind randomized controlled trial (RCT) design will be used in this study. A placebo group will be included parallel with the treatment group in this study. Forty IBD patients with mild to moderately active UC aged 18-65 will be recruited conveniently from the gastroenterology section, the IBD clinic at the Jordan University Hospital and Al-Bashir Hospital, Amman, Jordan. Patients who meet the inclusion criteria and agree to participate will be centrally

randomized to probiotic supplementation group or placebo group using computer-generated

random numbers, stratified by age and gender. The duration of intervention will be 6 weeks. **The**

study scheme:

The Interventions

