Palumbo *et al.*, 2016.

Ethical Approval:

This study will seek approval by Research Ethics Committee at the University of Jordan and by the Institution Research Board (IRB) of Jordan University Hospital and Al-Bashir Hospital, Amman, Jordan. The participants will be provided with information consent containing a brief description of the study and written informed consent will be obtained from all participants before their interview and blood drawl (10ml) (Appendix 1, 2). Participants' information will be treated confidentially. However, only the researcher (PhD student) will know participants' names and she is the only one who will give them identification (ID) number.

Personal Questionnaire:

The personal questionnaire will contain questions related to age, gender, education, employment, family income/month, residency area, smoking status, family history of IBD, medications, previous and current health problems. As well as, questions about using probiotics and certain eating habits will be asked (Appendix3). Anthropometric measurements including weight (measured to the nearest 0.1 kilogram) and height (measured to the nearest 1 cm) will be taken from the existing medical record. Body mass index (BMI) will be calculated.

Biochemical Measurements:

The researcher will take the permission form the participants to draw blood sample (10ml) and perform biochemical specialized labs. Venous blood samples will be withdrawn by specialized medical laboratory technicians. Complete blood count (CBC) will be analyzed using standard procedure. Blood serum will be separated by centrifugation (3000 rpm for 10 min) after clotting at room temperature (27 °C) and stored at -18°C until analysis. Immunoglobulin G(IgG), Immunoglobulin M (IgM), Immunoglobulin (IgA), interleukin (IL)-6, IL-1, IL-10, C-Reactive Protein (CRP), and TNF- α will be analyzed using commercially available enzyme-linked immunosorbent assay (ELISA) kits.

Data Collection and Quality of Life Questionnaire

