Three parts package was used for collecting data that met the purpose of this study, including a personal questionnaire, physical activity questionnaire, and a short inflammatory bowel disease questionnaire (SIBDQ). A face-to-face interview technique was used as a method for data collection. Data on age, body weight, educational level, previous and current health problems, family history of IBD, and probiotic use were collected. The physical activity level was measured using a 7-day Physical Activity Recall (PAR) which was originally developed by Sallis *et al.*, 1985 (Sallis *et al.*, 1985). For assessing the quality of life, a disease-specific, validated, and reliable Arabic version of the SIBDQ obtained from the McMaster short IBD questionnaire at McMaster University was used (Mahalli and Alharthi, 2017). The SIBDQ contains ten questions covering the four HRQOL domains (systemic, social, bowel, and emotional) which were calculated and scored. The response to each question of the ten was graded on a 7-point Likert scale ranging from 1 (worst aspect) to 7 (best aspect). The total SIBDQ scores range from 10 to 70, with higher scores indicating better HRQOL (Mahalli and Alharthi, 2017). The summation of the responses to Q4, Q6, and Q9 was used for the bowel domain, the sum of the responses to Q2 and Q3 was for the social domain, the sum of the responses to Q1 and Q7 was for the systemic domain, and the sum of the responses to Q5, Q8, and Q10 was for the emotional domain. The total score of SIBDQ was composed of the sum of the responses to all ten questions (Guyatt *et al.*, 1989; Mahalli and Alharthi, 2017).

Statistical Analysis:

Statistical analysis will be done using IBM SPSS Statistics 20.0 software (version 20.0, IBM, Inc., Chicago, IL, USA). Mean \pm standard deviation (SD) will be used to express the continuous data and percentage to express the categorical data. The categorical variables will be compared using the Chi square and the continuous variables will be compared using the one-way ANOVA. A

paired *t*-test will be used to assess within-group changes in outcomes from baseline to end of intervention. For all data, *P*< 0.05 will be considered statistically significant.

References

Abraham, B. P., and Quigley, E. M. (2017), Probiotics in inflammatory bowel disease. **Gastroenterology Clinics**, 46(4), 769-782.

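### Does the absence of a stated consequence for the Shapiro-Wilk check leave the between-group t-test on the serum markers unsound?

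*SAP*

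**What the plan says.** The SAP's Statistical Analysis section is a single paragraph in the past tense. For continuous variables it gives three elements in this order:

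- Summary: "Mean and standard deviation (SD) were calculated for the continuous variables".
- Check: "To check the normal distribution of continuous variables, the Shapiro-Wilk test was applied".
- Comparison between arms: "Independent samples T-test was used to detect differences between placebo and probiotics groups in terms of continuous variables".

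A paired t-test for within-arm change in the eight biochemical parameters follows, and then the significance level: "A p-value < 0.05 was considered statistically significant". The chi-square test is named for categorical data only. The section does not say what the normality check showed, or what would be done if it failed.

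The protocol's Statistical Analysis section offers no alternative. It has no normality check and says that "the continuous variables will be compared using the one-way ANOVA". With two arms, one-way ANOVA is the pooled t-test (F = t²). The Biochemical Measurements section says the immunoglobulins, interleukins, CRP and TNF-α "will be analyzed using commercially available enzyme-linked immunosorbent assay (ELISA) kits", and gives no distribution, SD or assay limit. On size, the Study Design section says "Forty IBD patients with mild to moderately active UC aged 18-65 will be recruited conveniently".

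**The concern.** A normality check with no stated consequence invites two questions: what did it show, and was it acted on? Inflammatory markers may have long right tails, and with about 20 patients per arm a few high values can inflate the SD and hide a real difference. The SAP names no transformation, no median and no rank test. The immune and inflammatory markers carry the first two of the trial's three objectives, and the documents contain no power calculation, so no stated margin exists to absorb lost efficiency. If the markers were log-normal, failed the check and were still compared on the raw scale, a null result on IL-6 or CRP could reflect an inefficient test rather than an ineffective supplement.

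**Working it through.** **Inputs from the documents.** 40 patients, two arms, significance level 0.05, between-group t-test. The plan states no power, effect size or SD, so it has no figure of its own to reproduce.

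**Assumptions.** 1:1 allocation (20 per arm), two-sided testing, values at a single time point, equal log-scale SD *s* in both arms, and *s* between 0.2 and 1.2.

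**Step 1: effect size.** For a two-sample t-test with n = 20 per arm, the degrees of freedom are 38, the critical value is 2.024 and the noncentrality is d × √(n/2) = d × √10. Power of 80% needs d = 0.909 (0.909 × 3.162 = 2.87). On the log scale this is a ratio of exp(−0.909 × *s*): for example 0.635 at *s* = 0.5 and 0.403 at *s* = 1.0.

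**Step 2: log-normal markers, effect set for 80% log-scale power** (40,000 simulated trials):

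| Log-scale SD | Raw t-test power | Log t-test power | Loss (points) | Raw type I error |
|---|---|---|---|---|
| 0.2 | 79.6% | 80.2% | 1 | 4.9% |
| 0.3 | 78.4% | 80.1% | 2 | 5.1% |
| 0.5 | 75.7% | 80.5% | 5 | 4.7% |
| 0.8 | 67.7% | 80.1% | 12 | 4.3% |
| 1.0 | 60.7% | 80.1% | 19 | 3.9% |
| 1.2 | 53.2% | 80.2% | 27 | 3.5% |

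The raw test does not produce excess false positives. The only possible harm is lost power, and it is material only from a log-scale SD of about 0.8.

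**Step 3: would the check have shown it?** With Shapiro-Wilk at 5% in each arm, both arms pass in 75%, 57%, 23%, 2.4%, 0.5% and 0.1% of trials, in the order of the table (8,000 trials). Where both pass, nothing is lost: raw against log power is 80% and 80%, 82% and 81%, 84% and 83% at 0.2, 0.3 and 0.5. Where the loss is 12 points or more, an analyst who ran the check would nearly always have seen a failure. (Testing per arm is also an assumption.)

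**Step 4: a different skewed shape.** Gamma-distributed markers with the scale halved in one arm, 20 per arm:

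| Gamma shape | Raw | Log | Rank | Raw minus log (points) |
|---|---|---|---|---|
| 1 | 51.3% | 39.6% | 44.0% | 12 |
| 2 | 83.6% | 76.2% | 78.4% | 7 |
| 4 | 98.7% | 97.7% | 97.8% | 1 |

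Here the raw t-test is the most powerful of the three. Skewness alone does not favour a log or rank analysis.

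**Step 5: the cost of adding tests.** Under the null with log-normal data, the chance that at least one of the raw, log and rank tests gives p < 0.05 is about 7% per marker, against 3.4% to 5.3% for the raw test alone (20,000 trials). The SAP analyses everything in both the intention-to-treat and per-protocol sets, so three tests on five markers would give 3 × 5 × 2 = 30 p-values with none named as decisive.

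**The case for a change.** The best case for a change is that the gap is real and cheap to close. The outcome of the check is the informative item: at a log-scale SD of 0.8 or more, a pass in both arms would be rare, so a reader shown the outcome would know whether the power loss is a live issue. For a true halving of a log-normal marker, raw against log power is 64% and 76% at a log-scale SD of 0.8, and 40% and 57% at 1.0. A log-scale ratio with a confidence interval needs no new measurements.

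The loss can also be larger than Step 2 shows. The SAP does not say whether arms are compared on end values or on change from baseline. With change scores, an assumed correlation of 0.5 and d = 0.909, power at a log-scale SD of 0.5 is 61% raw against 80% log.

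The arithmetic stands, and so does the observation that no rule is written down. The inference to a faulty plan does not. Harm needs three things the documents do not show: that the markers are close to log-normal, that they failed the check, and that the failure was set aside. The wording fits equally well with normality having been checked and accepted. Moving only the cytokines and CRP to the log scale, with the immunoglobulins left as they are, would also have no basis in the documents, which list all eight markers together without distributional information.

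**Conclusion.** No change to the plan is needed. The SAP leaves unsaid what would follow a failed Shapiro-Wilk test. Analysts ordinarily fill that gap, and the outcome of the check belongs in the results report. The named test keeps its type I error at or below the nominal level, apart from simulation noise. Its power relative to a log-scale test runs from a 27-point loss (log-normal, log-scale SD 1.2) to a 12-point gain (gamma, shape 1), and the documents cannot place these markers within that range. The choice of scale is therefore a fair trade-off. Adding log and rank tests as equals would bring a selection problem of about 7% per marker without a clear gain. These figures rest on 20 per arm, two-sided 5% testing and single-time-point values. The judgement would change if the reported results showed that markers clearly failed the check and only raw-scale comparisons were given.

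### The between-arm t-test is valid but takes no covariates; ANCOVA on baseline, age and gender would usually get more from the same 40 patients

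*SAP*

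**What the plan says.** The SAP (Statistical Analysis) has one sentence on comparing the arms for continuous outcomes: "Independent samples T-test was used to detect differences between placebo and probiotics groups in terms of continuous variables". The protocol (Statistical Analysis) says that "the continuous variables will be compared using the one-way ANOVA". Neither sentence names a time point, a change score or a covariate.

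Baseline is mentioned only for the within-arm tests. In the SAP, "A paired t-test was used to assess withingroup changes in biochemical parameters", listed as IgG, IgM, IgA, IL-1, IL-6, IL-10, TNF-α and CRP. In the protocol, a paired t-test "will be used to assess within-group changes in outcomes from baseline to end of intervention". Baseline values of all eight markers must therefore be available.

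The protocol (Study Design) plans "Forty IBD patients with mild to moderately active UC", allocated by computer-generated "random numbers, stratified by age and gender". Age and gender do not reappear in the statistical section of either document. The SAP's significance rule is: "A p-value < 0.05 was considered statistically significant".

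**The concern.** With about 20 patients per arm, precision is scarce. A marker value at the end of six weeks is likely to be related to the same patient's value at entry, and a covariate model removes that part of the variation from the treatment comparison. The plan has the data to do this and does not say that it will. Age and gender were thought important enough to stratify on, yet they are not carried into the analysis. At stake are wider confidence intervals and a greater chance of missing a real effect.

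There is a secondary gap. End value and change from baseline give different tests, and a chance baseline imbalance pushes them in opposite directions. A reader of the SAP cannot tell which one was planned.

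**Working it through.** The documents give no effect size, SD, power or sample-size calculation, so there is no planned figure to reproduce.

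**Inputs.** From the documents: 40 patients, significance at 0.05, stratification by age and gender. Assumed: 20 per arm (allocation ratio not stated), two-sided tests, normal data, equal SD at both visits, no dropout, and a true difference of 0.7 SD. The baseline-to-end correlation ρ is not given and is shown over a range.

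**Step 1: variance of each between-arm comparison** (SD = 1)
- End value: 1
- Change: 2(1 − ρ), which is 1.40 / 1.00 / 0.60 at ρ = 0.3 / 0.5 / 0.7
- ANCOVA on baseline: 1 − ρ², which is 0.91 / 0.75 / 0.51

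With a known slope, ANCOVA is never worse than either alternative. Its ratio to the change analysis is (1 + ρ)/2.

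**Step 2: power.** The noncentrality is 0.7 / √(variance × 2/20). For end values it is 0.7 / 0.316 = 2.21, which gives 57.8% on 38 degrees of freedom. The first two rows come from the noncentral t distribution. The ANCOVA rows are simulated with estimated slopes (40,000 trials per case), with age and gender taken as explaining nothing.

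| Analysis | ρ = 0 | 0.3 | 0.5 | 0.7 |
|---|---|---|---|---|
| End value | 58% | 58% | 58% | 58% |
| Change | 33% | 45% | 58% | 80% |
| ANCOVA, baseline only | 57% | 61% | 69% | 84–85% |
| ANCOVA, baseline + age + gender, balanced across arms | 56% | 60% | 69% | 84% |
| Same model, not balanced | 54% | 58% | 67% | 83% |

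The model with age and gender compares as follows:
- Against end values: a loss of about 1 to 3 points at ρ = 0, and a gain of 0 to 3, 9 to 11 and 25 to 26 points at ρ = 0.3, 0.5 and 0.7.
- Against change: a gain of 14 to 16, 9 to 11 and 3 to 5 points at ρ = 0.3, 0.5 and 0.7.
- If age and gender explained 10% of the remaining variance, its power would be 65% / 73% / 88% (balanced) or 63% / 71% / 86% (not balanced).

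Mean 95% CI width at ρ = 0.3 / 0.5 / 0.7 is 1.27 SD throughout for end values and 1.50 / 1.27 / 0.99 for change. For the model with age and gender it is 1.23 / 1.12 / 0.92 (balanced) or 1.27 / 1.15 / 0.95 (not balanced).

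**Step 3: ignoring the strata.** If the strata are balanced and explain a share R² of the variance, the t-test's standard error is too large by about 1/√(1 − R²). The actual error rate is then roughly 2Φ(−1.96/√(1 − R²)):
- R² = 0.10: 2Φ(−2.07) = 3.9%; simulated 3.8%
- R² = 0.20: 2Φ(−2.19) = 2.8%; simulated 2.8%

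The simulation used four strata of ten, split 5/5, and 100,000 trials.

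**Step 4: the unnamed variable.** With no treatment effect, the end-value and change statistics correlate at √((1 − ρ)/2), which is 0.71 at ρ = 0, 0.50 at 0.5 and 0.22 at 0.9. The chance that at least one has p < 0.05 is 8.3% at ρ = 0, 9.1% at 0.5 and 9.6% at 0.9. The ceiling for two independent tests is 1 − 0.95² = 9.75%. Either test alone, fixed in advance, holds about 5% when the strata are uninformative. At a true difference of 0.7 SD the two disagree on significance in 32% / 33% / 37% of trials at ρ = 0.3 / 0.5 / 0.7.

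**The case against.** The strongest reply is that an unadjusted two-group test is valid under randomisation, so ANCOVA is only a preference for efficiency. Its gain depends on ρ, the effect size, normality and complete follow-up, none of which the documents supply. The first part stands: nothing here makes the planned test wrong. The dependence on ρ also stands, and at ρ = 0.3 the gain over end values is small. But the possible loss is only a few points and the possible gain is large.

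A reader might infer that baseline goes unused altogether. The documents do not establish that. If the t-test is run on change, baseline enters by subtraction. What can be said is that no covariate adjustment is stated.

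A reader might also infer that the trial carries a 9% false-positive rate per marker. That would require running both tests and reporting the better one, and nothing in the documents shows this. The SAP speaks of change only for the paired tests, so a plausible though not certain reading is that measured values are compared between arms. The figure also assumes normality; with an illustrative lognormal distribution (log-SD 1, ρ = 0.5) it falls to 7.3%. It has nothing to do with the strata, whose omission makes the test conservative.

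Finally, a reader might infer that efficacy is to be judged from the paired tests. The plan does not say so, and it does include a between-arm test.

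**Conclusion.** The point holds as one of efficiency and should be fixed. The between-arm analysis is valid, but it states no adjustment for baseline values that the plan already requires or for the factors used in the randomisation. Under the assumptions listed, ANCOVA on baseline raises power from 58% (end values) to about 61% / 69% / 85% at ρ = 0.3 / 0.5 / 0.7, and it also exceeds the change analysis at each of these values. If age and gender are balanced and prognostic, ignoring them brings the actual error rate below the nominal 5%, to about 3.8% or 2.8% when they explain 10% or 20% of the variance.

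The unnamed variable is secondary. It would lead to a false-positive rate of about 8% to 10% per marker only if the choice between end value and change were made after seeing both. Confidence is high that covariates and the tested variable are not stated. The size of the gain is conditional on ρ.

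**What to change.** For each of the eight markers, define the between-arm estimate as an ANCOVA of the end-of-study value on treatment, the baseline value of the same marker, and age and gender in the form used for the randomisation. Report the adjusted difference, its 95% CI and the p-value. Do the same for the SIBDQ, which serves the third objective, if a baseline score was taken; the protocol's questionnaire section does not say when it was given. If the Shapiro-Wilk check already in the SAP indicates skew, fit the model on the log scale. State that the within-arm paired tests are descriptive and carry no treatment claim.

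The SAP is written in the past tense. If the data have already been analysed, state which variable the t-test used, keep that result as the planned one, and show the ANCOVA beside it, labelled post hoc.

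The cost is a few lines of SAP text and one regression per outcome in SPSS, with no new patients; the markers need no new data. Adding age and gender to the baseline-only model costs under 1 point of power if they are balanced across arms and about 2 to 2.5 points if not. If ρ is near zero, the full model is about 1 to 3 points worse than the end-value t-test.

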2012a). UC is a lifetime disease that is characterized by periods of remission and periods of relapse. The relapsing periods often presented with a combination of rectal bleeding, diarrhea, abdominal pain, malaise and weight loss, which are responsible for the decreased quality of life and for most of the disease burden (Dignass *et al.*, 2012b; Levesque *et al.*, 2015). Moreover, newly diagnosed UC patients have a 5-year risk of colectomy of 10–35% (Van Assche *et al.*, 2013), and ultimately, the extensive and persistent inflammation can increase the long-term risk of colorectal cancer (Van Assche *et al.*, 2013). Worldwide, UC is reported to have an overall prevalence range from 7.6 to 245 cases per 10 0,0 0 0 persons/year and an incidence of 1.2–20.3 cases per 10 0,0 0 0 persons/year (Ng *et al.*, 2017; Feuerstein *et al.*, 2019; Gajendran *et al.*, 2019). For specific countries, the UC prevalence in the United States was 286 cases per 100,000 populations (Kaplan and Ng, 2016), in San Marino was 311 per 100,000 populations (Piscaglia *et al.*, 2019), and in Norway 505 of 100,000 populations (Ng *et al.*, 2017). In Jordan, there have been no studies conducted on the prevalence of UC. However, the incidence of UC is growing in Jordan, with changes in the cultural behavior influenced by Westernization and now converted to a country with varied ethnicities (Omran and Barakat, 2016).

The Food and Agriculture Organization of the United Nations (FAO) and the World Health Organization (WHO) nutritional guidelines have defined probiotics as “live microorganisms when administered in adequate quantities confer a health profit to the host cell” (Araya *et al.*, 2002; FAO/WHO, 2013; Nolfo *et al.*, 2013). Probiotics have been used in IBD and especially UC (Sartor, 2004). The effect of using probiotics on UC has been studied in a variety of experimental conditions both in vitro and in vivo (Abraham and Quigley 2017; Guandalini and Sansotta, 2019). The rational explanation for using probiotics in UC is based on the hypothesis that intestinal bacteria might be associated with the pathogenesis of IBD in general, and UC in specific (Sartor, 2004). Balance disturbance between the host’s genetic background, enteric microflora, and bowel mucosal immunity might be involved in tissue inflammation in UC (Naidoo *et al.*, 2011).

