movements and cessation of bleeding (Dignass *et al.*, 2012b; Vanga and Long, 2018). The suitable treatment approach for each patient is personalized based on the activity, distribution (proctitis, left-sided, extensive), pattern of disease (relapse frequency, course of disease, response to previous medications, side-effect profile of medication and extra-intestinal manifestations) and the age at onset and disease duration (Dignass *et al.*, 2012b). Most patients are treated with pharmacological therapy to first induce remission and then to maintain a corticosteroid-free remission. There are multiple classes of drugs used to treat the disease (Vanga, and Long, 2018). However, the patients in which medical therapy fails or have developed dysplasia secondary to their long-standing colitis require surgical treatment (Ray and Sagar, 2017; Feuerstein *et al.*, 2019).

In addition to the progression in the treatment of inflammatory bowel diseases (IBD) specially UC, adjuvant and alternative options are continually seeking and needed to enhance and improve the pharmacological treatment (Guandalini and Sansotta, 2019). These options include dietary modifications, food supplements, and, more recently, probiotics (Guandalini and Sansotta, 2019). Mucosal homeostasis or chronic inflammation are occurring as a result of the imbalance between beneficial and harmful intestinal microorganisms which known to be associated with IBD occurrences (Guandalini and Sansotta, 2019). The UC and IBD patient's microbiota differ from healthy individuals, as it is characterized by a reduced diversity, reduced abundance of *Firmicutes* and *Bacteroidetes*, and increased the abundance of *Enterobacteriaceae* (Guandalini and Sansotta, 2019).

Probiotics

As the demands for healthy and functional foods that promote health and prevent or cure illness increased during the last decades, probiotics have received attention in the field of self-care and complementary medicine (Shokryazdan *et al.*, 2017a). The word “probiotic” comes from the

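### The only test tied to baseline-to-end change is a within-arm paired t-test; the planned between-arm test is not tied to week-6 or change values, and neither is named as the basis for efficacy

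*SAP*

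**What the plan says.** All three objectives in the protocol ask for the effect of the probiotic: on immune response, on inflammatory response and on quality of life. The Statistical Analysis sections then plan two kinds of test for continuous data.

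- **Between arms.** SAP: "Independent samples T-test was used to detect differences between placebo and probiotics groups in terms of continuous variables". Protocol: "the continuous variables will be compared using the one-way ANOVA". Neither sentence says whether the values compared are baseline, week-6 or change values, and neither adjusts for baseline.
- **Within arms.** SAP: "A paired t-test was used to assess withingroup changes in biochemical parameters", listing eight markers (IgG, IgM, IgA, IL-1, IL-6, IL-10, TNF-α and CRP). Protocol: a paired t-test "will be used to assess within-group changes in outcomes from baseline to end of intervention".

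The within-arm test is therefore the only one that either document links to change over the six weeks. A single threshold, p < 0.05, applies to all tests. No primary outcome, primary test or decision rule says which p-value answers the objectives.

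**The concern.** A randomised placebo arm lets the analyst subtract whatever would have happened anyway. A paired test inside one arm does not make that subtraction.

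The protocol gives reasons to expect something to subtract. Under The Research Problem it says that "UC is a lifetime disease that is characterized by periods of remission and periods of relapse". Under Study Design it recruits patients with mild to moderately active disease, and the objectives call them pre-remission. Patients selected while active may improve through the natural course or through regression to the mean, in both arms alike. Inflammatory markers could then fall significantly in the probiotic arm with no contribution from the probiotic.

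The plan does not rank the tests. If the paired test is significant and the between-arm comparison is not, nothing in either document says which one the conclusion follows. Nor does anything rule out the inference that a result significant in one arm and not in the other shows an effect. That pattern is not a test of the difference between arms.

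**Working it through.** **Plan's own figure.** The protocol states 40 patients but gives no effect size, SD or power, so there is no calculation to reproduce.

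**Inputs from the documents.** 40 patients in total; six weeks of intervention; eight markers in the SAP's paired test; threshold 0.05.

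**Assumptions not in the documents.** Equal allocation (20 per arm); two-sided tests; no dropout; independent arms; approximately normal change scores; no probiotic effect; and the same mean improvement in both arms, d, in SDs of the change score. The documents give no value for d, so a range from 0 to 0.8 is shown.

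**Step 1: paired test in one arm.** With n = 20 the test has 19 degrees of freedom and a two-sided 5% critical value of 2.093. Under a shift d the statistic follows a noncentral t distribution with noncentrality d × √20. At d = 0.5 this is 0.5 × 4.472 = 2.236. The chance of significant improvement is

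P_imp = P(T > 2.093), T noncentral t with 19 df and noncentrality d√20.

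**Step 2: probiotic significant, placebo not.** Write P_sig for the chance of significance in either direction. As the arms are independent with the same shift, the chance is P_imp × (1 − P_sig). At d = 0.5: 0.564 × (1 − 0.565) ≈ 0.246 (unrounded inputs).

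**Step 3: between-arm test of change.** The expected difference in mean change is d − d = 0 for any d, so the test keeps its nominal rate. Simulation of 50,000 trials gave 4.9%, 5.2% and 5.0% at d = 0, 0.5 and 0.8.

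| Common shift d | Noncentrality | Probiotic arm significantly improved | Probiotic significant, placebo not | Between-arm test of change, two-sided |
|---|---|---|---|---|
| 0 | 0 | 2.5% | 2.4% | about 5% |
| 0.3 | 1.342 | 24.6% | 18.6% | about 5% |
| 0.5 | 2.236 | 56.4% | 24.6% | about 5% |
| 0.8 | 3.578 | 92.4% | 7.0% | about 5% |

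The figures are per marker. In the direction of benefit, the between-arm rate is half of 5%, or 2.5%.

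**Step 4: fewer completers.** With 15 per arm and d = 0.5 the two paired-test figures are 43.8% and 24.6%, so moderate dropout does not remove the problem.

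The last paired column falls at large d because both arms become significant. At d = 0.8 the misreading at risk is the simpler one: taking the probiotic arm's own significant change as an effect.

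**The case against.** The strongest reply is that a randomised comparison is already planned. The SAP sentence just before the paired t-test compares placebo with probiotic, and the protocol plans an ANOVA. The markers are continuous variables, so both sentences can cover week-6 data. A supplementary paired test does not cancel that comparison. This stands: a reader might infer that no between-arm test is planned, and that would be wrong. What remains is that either sentence could be satisfied by comparing baseline characteristics alone, and neither has precedence over the paired test.

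Second, both documents say only that the paired test assesses within-group change, which it does validly. A reader might infer that the trial will judge efficacy from it. Neither document says so, nor that significance in one arm only counts as success. This also stands. The documents are silent on which test supports efficacy; they do not choose the wrong one. The 25%, 56% and 92% are accordingly not false rejections by the paired test, which would be detecting a real change within the arm. They become error rates only if that change is credited to the probiotic.

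Third, the size of the common shift is assumed. The protocol supports fluctuation but gives no magnitude or six-week time course, and nothing suggests that serum IgG, IgM or IgA would shift as much as CRP or the cytokines. At d = 0 the inflation disappears.

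Fourth, a reader might infer that participants are known to be recovering on newly started drug treatment. The protocol's account of drug therapy to induce remission is general literature, not a description of those enrolled. The eligibility criteria do not require such therapy, and they exclude some recent changes in it. The point therefore rests on active relapsing-remitting disease at entry, not on treatment-induced recovery.

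**Conclusion.** The concern holds as a gap in specification and interpretation. The within-arm paired test is the only analysis tied to baseline-to-end change, the between-arm test has no stated time point or form, and nothing says which one answers the objectives.

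If a paired result were read as efficacy, the chance per marker of crediting the probiotic with a shared improvement would be 25%, 56% or 92% at a common shift of 0.3, 0.5 or 0.8 SD, against 2.5% with no shift. If the claim required significance in the probiotic arm only, the figures would be 19%, 25% or 7%, against 2.4%. These depend on the assumptions listed and on that misreading. A between-arm test of change is immune to the common shift.

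The plan should be fixed on this point. It is not a fatal defect, because a randomised comparison is already listed and no rule bases efficacy on the paired tests.

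**What to change.** In both documents:

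- State that conclusions about the effect of the probiotic rest only on the between-arm contrast at week 6, reported as an estimate with a 95% CI.
- Define that contrast as either the difference in change from baseline or the difference in week-6 value adjusted for baseline by ANCOVA. Without this definition, relabelling the paired tests would leave the efficacy analysis unspecified.
- Keep within-arm changes as description: mean change with a 95% CI per arm, no significance label, and no comparison of p-values between arms.

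The SAP is written in the past tense, so this should be a dated clarification applied to reporting.

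The cost is wording and, where the contrast has not yet been run in this form, a re-analysis of data already collected. The small downside is that a significant within-arm change can no longer be reported as a finding.
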